#### Dose-Limiting Toxicities

Hematologic Toxicity
• Grade 3 thrombocytopenia associated with clinically significant bleeding and requiring platelet transfusion or Grade 4 thrombocytopenia of any duration
• Grade $\geq 3$ febrile neutropenia
• Grade $\geq 3$ anemia requiring a blood transfusion
• Other Grade $\geq 4$ toxicity, excluding toxicities listed below this table
Nonhematologic Toxicity – Nonlaboratory
• Grade $\geq 3$ irAE
• Grade $\geq 3$ colitis or noninfectious pneumonitis
• Grade $\geq 3$ pneumonitis or Grade 2 pneumonitis that does not show clinical improvement within 3 days after initiation of optimal medical management including corticosteroids therapy, which is then treated as Grade 3
• Grade $\geq 3$ nausea, vomiting or diarrhea that lasts more than 48 hrs despite optimal supportive care
• Grade $\geq 3$ fatigue lasting $>7$ days
• Grade $\geq 3$ hypertension despite maximal medical therapy
• Grade $\geq 3$ tachycardia
• Any other Grade $\geq 3$ toxicity
• Immune-related adverse event that necessitated permanent discontinuation of study drug(s), regardless of grade
Nonhematologic Toxicity – Laboratory/Investigations
• Any Grade $\geq 3$ laboratory abnormality except for specific exceptions listed below
• ALT or AST: 
 
○ <math>>8 \times</math> ULN
 
○ <math>\geq 2</math>-fold above the patient's baseline value that lasts <math>>7</math> days,
 
○ <math>\geq 3 \times</math> ULN with concomitant bilirubin <math>>2 \times</math> ULN, in the absence of cholestasis
 
○ Total bilirubin <math>>3 \times</math> ULN
 
○ <math>\geq</math>Grade 3 amylase or lipase that is associated with symptoms or clinical manifestations of pancreatitis
 

Please refer to Section 8.2.1.1 for additional hepatic safety monitoring guidance.

**Other Hematologic or Nonhematologic Toxicity That May Be a DLT.**

- Toxicity deemed by the investigator and Lilly CRP to be dose limiting, such as:
  - toxicity that is possibly related to study treatment and requires discontinuation of the patient from the study at any time within the DLT observation period, or
  - persistent Grade >2 toxicities causing a delay of LY3475070 study treatment >14 days during the DLT observation period.

Abbreviations: AE = adverse event; ALT = alanine transaminase; AST = aspartate transaminase; CRP = clinical research physician; HCC = hepatocellular carcinoma; irAE = immune-related adverse event; IV = intravenous; ULN = upper limit of normal.

**The following adverse events are not considered DLTs:**

- Toxicity that is clearly and directly related to the primary disease or to another etiology
- Grade 3 endocrine disorder (thyroid, pituitary, and/or adrenal insufficiency), if both the following criteria are met:
  - the disorder is manageable with or without systemic corticosteroid therapy and/or hormone replacement therapy, and
  - the patient is asymptomatic
- Grade 3 inflammatory reaction attributed to a local antitumor response (such as, inflammatory reaction in the lymph nodes or at sites of metastatic disease)
- Any grade vitiligo or alopecia
- $\geq$ Grade 3 electrolyte abnormality that lasts <72 hours, is not clinically complicated and resolves spontaneous or responds to conventional medical interventions
- $\geq$ Grade 3 amylase or lipase that is not associated with symptoms or clinical manifestations of pancreatitis
- Grade 3 or 4 neutropenia, provided **both** of the following criteria are met:
  - is not associated with fever or systemic infection, and
  - improves by at least 1 grade within 5 days
- Grade 3 or 4 lymphopenia

**6.1.1.2. DLT-ET**

A **DLT-equivalent toxicity (ET)** is any event listed in Section 6.1.1.1 occurring after the DLT observation period in Phase 1a or any cycle in Phase 1b.

A DLT-ET is an AE that meets the DLT criteria as defined above and occurs in any cycle other than the DLT assessment period (28 days for Cohorts A1 through A4 and B1 through B3). In addition to the DLT assessment period, available safety data beyond the DLT assessment period may also be taken into consideration prior to a decision to advance to the next DL or the determination of the RP2D.

Potential DLTs that are AEs, which are reasonably anticipated AEs for concomitant medication should be reviewed by the treating investigator and Lilly CRP/CRS before final determination as a DLT. Review and discussion may include additional participating investigators. Such review

may determine that confounding factors render the case to be not evaluable for the purposes of dose selection.

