This study is designed to identify a DL with a dose-limiting target toxicity rate of 30%. The mTPI-2 method considers an equivalence interval (EI) around the target toxicity rate. For this study, the EI is elicited to be (25%, 35%), resulting in the rules below.

Safety data, in particular DLTs, will be the primary criteria for the dose escalation. In addition, if available at the time of dose escalation decision, PK/pharmacodynamics results (for example,  $C_{max}$ , area under the concentration curve (AUC), pharmacodynamics results) will be used as secondary/supporting data for dose escalation.

Intermediate and/or higher dose as well as alternative schedules of administration will be explored if deemed necessary after discussion between Lilly and investigators and taking into account patient safety and PK/pharmacodynamics data. If needed, additional patients may be enrolled to further assess PK/pharmacodynamics or tolerability.

In order to be DLT-evaluable, patients must have received 75% of LY3475070 scheduled dose within the 28-day DLT period unless patients have a DLT qualifying event. For patients treated with the combination treatment, patients must have received 75% of LY3475070 and a minimum of 1 pembrolizumab infusion within the 28-day DLT period.

In the dose escalation phase, once a given DL is cleared for DLT evaluation and is deemed safe, the dose cohort may be expanded to further investigate the safety, PK, pharmacodynamic, and clinical activity of LY3475070 and the combination with pembrolizumab. There will be up to 20 backfill patients enrolled across all dose levels in cohorts A and B combined in the phase 1a study. Any AEs reported by those backfilled patients that meet the DLT criteria as defined in Section 6.1.1.1 and occur in the DLT period are considered DLT-equivalent toxicities (Section 6.1.1.2). The cumulative safety data from the cohorts previously declared safe and the current dose cohort under evaluation will be continuously monitored. A Bayesian toxicity monitoring rule will be implemented for DLT-equivalent toxicities added from backfill patients (Section 9.2). These aggregate safety data will be included in defining the RP2D.

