### 6.1.1. Definition of DLT and DLT-ET

#### 6.1.1.1. DLT

A DLT is defined as any of the events listed in the table below, if both of the following criteria are met:

- the event occurs during the DLT observation period (28 days) in Phase 1a, and
- the event cannot, in the opinion of the investigator, be definitely attributed to primary disease or extraneous causes, such as accident.

Patients who experience a DLT in the DLT observation period will be discontinued from study treatment.

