### 10.8. Appendix 8: Dose-Finding Algorithm of the Modified Toxicity Probability Interval-2 Method Showing Number of Patients Treated

$n = 20, p_T = 0.3, \epsilon_1 = 0.05, \epsilon_2 = 0.05$

**E**: Escalate to the next higher dose; **S**: Stay at the same dose; **D**: De-escalate to the previous lower dose; **DU**: De-escalate to the previous lower dose and the current dose will never be used again in the trial;

\* If at the first dose level, users can choose to early-terminate the trial or not based on their own discretion.

The number of patients dosed at a given DL is shown in the columns (X-axis), while the number of DLTs experienced is shown in the rows (Y-axis). The rules in this figure will be used for each DL evaluated; the patient numbers and DLTs do not carry over from cohort to cohort. By locating the intersection of the number of patients dosed and the number of DLTs, 1 of 4 predefined rules is used:

- E: Escalate the dose
- S: Stay at the same dose
- D: De-escalate the dose
- DU: De-escalate the dose due to unacceptable toxicity. The dose cannot be re-escalated to this DL at a future point in the escalation.

For example, within a cohort:

- If 1 of 3 patients experiences a DLT, stay at the same dose (see “S” in column 3, row 1). The fourth patient must be treated at the same DL.
- If 1 of 6 patients experiences a DLT, escalate the dose (see “E” at column 6, row 1).
- If 2 of 3 patients experience a DLT the dose to treat the next patient is de-escalated (see “D” at column 3, row 2).
- If 5 of 7 patients experience a DLT, the dose is determined to be unacceptably toxic, and the previous dose is defined as the MTD.

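### Protocol 6.1.1.2 lets confounded potential DLTs leave the dose-escalation count as not evaluable, although 6.1.1.1 counts listed events whose attribution is uncertain

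*Protocol*

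**What the plan says.** Protocol Section 6.1.1.1 defines a DLT as an event on its list that meets two conditions: it falls in the 28-day observation period of Phase 1a, and "the event cannot, in the opinion of the investigator, be definitely attributed to primary disease or extraneous causes, such as accident". The list of events not considered DLTs has a matching exemption: "Toxicity that is clearly and directly related to the primary disease or to another etiology".

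Section 6.1.1.2, under the DLT-ET heading, adds a step that governs DLTs as well. Potential DLTs that are "reasonably anticipated AEs for concomitant medication should be reviewed by the treating investigator and Lilly CRP/CRS before final determination as a DLT". Other investigators may join the discussion. The review "may determine that confounding factors render the case to be not evaluable for the purposes of dose selection".

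Evaluability is defined in three places. Protocol 4.1.1 requires 75% of scheduled LY3475070 doses "within the 28-day DLT period unless patients have a DLT qualifying event", plus at least one pembrolizumab infusion for combination patients. Protocol 9.3 uses 3 weeks of follow-up and treatment, or earlier discontinuation for a DLT. SAP Table JZMA.6.1 uses 28 days and 75% of doses, or earlier discontinuation for a DLT. None of them mentions confounding.

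**The concern.** Two standards apply to the same event. Under 6.1.1.1 doubt about the cause leaves the event in the count, because only definite attribution elsewhere takes it out. Under 6.1.1.2 doubt about the cause can take it out. A patient removed in this way is neither a DLT nor a non-DLT in the mTPI-2 tally.

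The removal depends on the outcome, since a patient without a potential DLT never reaches this review. DLTs are a Phase 1a primary endpoint and the primary criterion for escalation (4.1.1), so the tally feeds the MTD and the dose taken into Phase 1b. The documents do not define confounding, do not say whether the patient is replaced, and ask for no tally with the case counted. The SAP does not mention the route, and there is no data monitoring committee.

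**Working it through.** **1. Which cases the route affects**

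| Attribution of a listed event in the window | 6.1.1.1 and exemption list | 6.1.1.2 review |
|---|---|---|
| Definitely or clearly due to something else | Not a DLT | Adds nothing |
| Uncertain (confounded) | DLT | May become not evaluable |
| No competing anticipated cause | DLT | Review not triggered |

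Only the middle row differs, and there the two sections point in opposite directions.

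**2. Direction.** With x DLTs among n patients, removing one DLT case gives (x−1)/(n−1) without replacement, which is at most x/n. With replacement it gives (x−1)/n if the new patient has no DLT, or x/n if that patient has one. The counted rate falls or stays the same; it cannot rise.

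**3. Reproducing the plan's decisions.** Inputs from 4.1.1 and Appendix 8 are a target of 0.30 and an equivalence interval of 0.25 to 0.35. The decision table is a figure that was not available, so I assumed a Beta(1,1) prior and a DU cut-off of P(p > 0.30) > 0.95. The posterior is Beta(1+x, 1+n−x). The decision is the sub-interval (width 0.10, shorter at the ends) with the highest posterior probability per unit width. This returns all five decisions that the protocol states in words: 1/3 stay, 1/6 escalate, 2/3 de-escalate, 5/7 DU (Appendix 8) and 2/6 stay (4.1.1). For example, Appendix 8 says "If 1 of 3 patients experiences a DLT, stay at the same dose".

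**4. Effect of one removed case** (cells marked * are recomputed and not stated in words)

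| Case counted | Replaced by a DLT-free patient | Not replaced |
|---|---|---|
| 1/3 stay | 0/3 escalate* | 0/2, below the minimum of 3 |
| 2/3 de-escalate | 1/3 stay | 1/2 de-escalate* |
| 2/6 stay | 1/6 escalate | 1/5 escalate* |
| 4/6 DU* | 3/6 de-escalate* | 3/5 de-escalate* |

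The 2/3 example therefore depends on a replacement being treated, whereas 2/6 shifts either way. In the last row the bar on returning to that dose disappears.

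**5. Section 9.2 monitoring rule.** Its table pauses at 2 or more among 4–5 patients and at 3 or more among 6–8. So 3/6 pauses but 2/6 (removed, replaced by a DLT-free patient) does not; 2/5 pauses but 1/4 (removed, not replaced) does not. Removing a case from 3/6 without replacement leaves 2/5, which still pauses. The protocol does not say whether a case that is not evaluable for dose selection also leaves this tally.

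**6. Illustrative operating effect.** Let p be the true DLT rate and f the share of true DLTs declared not evaluable and replaced. The apparent rate is q = p(1−f)/(1−pf). Both p = 0.40 and f are assumptions; the documents give neither.

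| f | q | P(0/3) = (1−q)³ | P(≤1/6) = (1−q)⁶ + 6q(1−q)⁵ |
|---|---|---|---|
| 0 | 0.400 | 0.216 | 0.233 |
| 0.25 | 0.30/0.90 = 0.333 | 0.296 | 0.351 |
| 0.50 | 0.20/0.80 = 0.250 | 0.422 | 0.534 |

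**The case against.** The best defence is that 6.1.1.2 concerns potential DLTs before final determination. Being an anticipated effect of a concomitant drug only triggers the review; it does not by itself remove the case. Nothing says that the review overrides 6.1.1.1. That is fair as to intent, but an event can already satisfy 6.1.1.1 in full when it reaches the review, and the stated ground for removal is confounding, which is short of definite attribution.

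Three further points stand as limits. First, the mTPI-2 table does not decide alone: 4.1 has the totality of safety data reviewed before escalation, 4.1.1 allows a more conservative choice than the table, and the event remains in the adverse event summaries. This softens the effect but does not put the case back in the tally. Second, other rules push the other way. The 75% dosing rule removes under-dosed patients without a DLT and keeps those with one, and the protocol lets the investigator and sponsor physician deem a possibly related toxicity dose limiting. The direction shown here belongs to this route, not to the whole trial. Third, a replacement patient may also have a DLT, in which case the decision is unchanged.

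A reader might also infer that 4.1.1 flatly contradicts 6.1.1.2 by keeping every patient with a DLT-qualifying event evaluable. It does not: the clause waives the 75% dosing requirement and is silent on confounded cases. Nor do the documents say how many patients take medication that could trigger the review, so they do not support a claim that most listed DLTs are exposed to it.

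**Conclusion.** The point holds for listed events within the 28-day period whose attribution is uncertain. Sections 6.1.1.1 and 6.1.1.2 treat these differently, the not-evaluable category is absent from all three evaluability definitions, and using it can move the tally only towards a lower DLT rate. One case is enough to change a decision: 2/6 to 1/6 and 2/3 to 1/3 rest on decisions written in the protocol, given a DLT-free replacement; 1/3 to 0/3 rests on recomputation.

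The probabilities are illustrations. At an assumed true rate of 40%, the chance of 0/3 is 22% with no removals, 30% with a quarter removed and 42% with half removed. How often the route would be used is unknown, so the documents do not support a statement that the MTD will be biased by any given amount. It would also go too far to conclude that every ambiguous event must be declared a DLT for all purposes: 6.1.1.1 ties a DLT to stopping study treatment, which is a separate matter from the tally.

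**What to change.** Reconcile Protocol 6.1.1.1, its list of events not considered DLTs, 6.1.1.2, 4.1.1, 9.3 and SAP Table JZMA.6.1, so that one attribution standard and one evaluability definition govern both the mTPI-2 tally and the Section 9.2 monitoring rule. For those tallies, a reviewed case that meets 6.1.1.1 and is not definitely attributed elsewhere should not drop out as not evaluable. State how reviewed cases enter the numerator and denominator, and whether such patients are replaced.

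At minimum, list every case reviewed under 6.1.1.2 and, before each escalation decision, show the mTPI-2 and Section 9.2 results with it counted as a DLT. What the classification means for the individual patient's treatment under 6.1.1.1 is for the sponsor to reconcile.

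The cost is a few sentences in the protocol, a matching line in the SAP and no new data. The downside is that some ambiguous events count, so escalation becomes slightly more conservative.

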### **6.1.2. Definition of RP2D**

The RP2D will be chosen following discussion between the Lilly CRP/CRS and the investigators based on consideration of the totality of the data during interim analyses and upon completion of Phase 1, including but not limited to LY3475070 dose adjustments, AEs, chronic intolerance, PK/pharmacodynamics data, and irAEs.

## **6.2. Preparation/Handling/Storage/Accountability**

1. The investigator or designee must confirm appropriate temperature conditions have been maintained during transit for all study intervention received and any discrepancies are reported and resolved before use of the study intervention.
2. Only participants enrolled in the study may receive study intervention and only authorized site staff may supply or administer study intervention. All study intervention must be stored in a secure, environmentally controlled, and monitored (manual or automated) area in accordance with the labeled storage conditions with access limited to the investigator and authorized site staff.
3. The investigator, institution, or the head of the medical institution (where applicable) is responsible for study intervention accountability, reconciliation, and record maintenance (i.e., receipt, reconciliation, and final disposition records).
4. Further guidance and information for the final disposition of unused study interventions are provided in the Pharmacy Manual.
5. Investigators should consult the site training, Pharmacy Manual or label for the specific study drug information.

## **6.3. Measures to Minimize Bias: Randomization and Blinding**

This is an open-label dose finding study.

The Phase 1b dose expansion part will implement a randomization design for Cohorts C and D to mitigate the selection bias in allocating patients to either monotherapy dose expansion or combination therapy dose expansion.

## **6.4. Study Intervention Compliance**

Participant compliance with study intervention will be assessed at each visit. Compliance will be assessed by direct questioning, counting returned capsules/tablets/packages, and reviewing patient diaries. Deviation(s) from the prescribed dosage regimen should be recorded in the eCRF. Seventy-five percent of LY3475070 treatment doses must have been received by the patient in order to be considered compliant.

For IV medication, study intervention that is administered intravenously will be administered only at the investigational sites by the authorized study personnel. As a result, treatment compliance is ensured.

## 6.5. Concomitant Therapy

At baseline, record prior and concurrent medications. Record all premedication, supportive care, and concomitant medication continuously at every visit and throughout the study.

The Lilly CRP/CRS should be contacted if there are any questions regarding concomitant or prior therapy. Patients with metastatic CRPC may continue with luteinizing hormone-releasing hormone analogue for testosterone suppression. Zoledronic acid or denosumab given for bone support is allowed to be continued if started 1 week prior to study treatment dosing. However, zoledronic acid or denosumab should not be initiated, especially in metastatic CRPC patients, after study treatment has commenced. No other chemotherapy, immunotherapy, herbal supplements and/or herbal drugs intended to treat cancer, or experimental drugs will be permitted while the patients are in this study.

CCI

If patients can't be switched to alternative therapy Lilly CRP/CRS must be consulted. For a list please consult Appendix 5. Immune-suppressive glucocorticosteroids other than to treat treatment related irAE are also prohibited.

Administration of live vaccines is prohibited during the study and for 3 months following the final dose of study drug. Any medication or vaccine (including over-the-counter or prescription medicines, vitamins, and/or herbal supplements) that the participant is receiving at the time of enrollment or receives during the study must be recorded along with:

- Reason for use
- Dates of administration including start and end dates

Medications or vaccinations specifically prohibited in the exclusion criteria are not allowed during the ongoing trial. If there is a clinical indication for any medication or vaccination specifically prohibited during the trial, discontinuation from trial therapy or vaccination may be required. The investigator should discuss any questions regarding this with the Sponsor. The final decision on any supportive therapy or vaccination rests with the investigator and/or the participant's primary physician. However, the decision to continue the participant on study treatment requires the mutual agreement of the investigator, Lilly CRP/CRS, and the participant.

Listed below are specific restrictions for concomitant therapy or vaccination during the course of the study:

- Antineoplastic systemic chemotherapy or biological therapy
- Immunotherapy not specified in this protocol
- Chemotherapy not specified in this protocol
- Investigational agents other than pembrolizumab
- Radiation therapy

Note: Radiation therapy to a symptomatic solitary lesion or to the brain may be allowed at the investigator's discretion.

- Live vaccines within 30 days prior to the first dose of study treatment and while participating in the study. Examples of live vaccines include, but are not limited to, the following: measles, mumps, rubella, varicella/zoster, yellow fever, rabies, BCG, and typhoid vaccine. Seasonal influenza vaccines for injection are generally killed virus vaccines and are allowed; however, intranasal influenza vaccines are live attenuated vaccines and are not allowed.
- Systemic glucocorticoids for any purpose other than to modulate symptoms from an AE that is suspected to have an immunologic etiology. The use of physiologic doses of corticosteroids may be approved after consultation with the Lilly CRP/CRS.

Note: Inhaled steroids are allowed for management of asthma.

Participants who, in the assessment of the investigator, require the use of any of the aforementioned treatments for clinical management should be removed from the study.

All treatments that the investigator considers necessary for a participant's welfare may be administered at the discretion of the investigator in keeping with the community standards of medical care.

All concomitant medication will be recorded on the eCRF including all prescription, over-the-counter products, herbal supplements, and IV medications and fluids. If changes occur during the study period, documentation of drug dosage, frequency, route, and date should also be included on the eCRF.

All concomitant medications received within 28 days prior to the first dose of study treatment and up to 90 days after the last dose of study treatment should be recorded. Concomitant medications administered up to 90 days after the last dose of study treatment should be recorded for SAEs and events of clinical interest (Section 8.3.7).

